#### 5.3.1 Last Observation Carried Forward

Imputation for missing observations will be applied to selected efficacy endpoints by using the last observation carried forward method. For subjects who withdraw from the study, the last valid observation recorded on treatment (scheduled or unscheduled) will be carried forward to all remaining visits. Also, for subjects in efficacy analyses who had missing observations prior to their last observation on treatment, the closest previous non-missing on-treatment observation will be carried forward to missing visits. If a subject had missing observation(s) immediately after baseline, the baseline observation will not be carried forward and the visit(s) will be left as missing.

In general, the LOCF method will be used for all efficacy endpoints that are evaluated at or before Week 24. Beyond Week 24, all analyses will not impute any missing data; this non-imputation method will be referred to as the observed case (OC). The descriptive summaries of endpoints by study medication group will include the count of missing values at each visit. The detail of which analysis utilizes LOCF algorithm is available in Section 7.

It is expected that 24 weeks of treatment is required to obtain the full treatment effect; shorter treatment periods may result in the observation of only a partial (smaller) treatment effect. Therefore, assuming that subject discontinuation of study drug or early termination from study will occur equally and at random in both treatment groups and in each stratum, this LOCF imputation approach is expected to provide a statistically conservative estimate for the treatment effect.

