### 7.3 Exploratory Efficacy Analyses

#### 7.3.1 Repeated Measures Analyses

To assess treatment as an effect over time on HbA1c change from baseline, a repeated measures analysis will be performed in supportive of the primary and secondary efficacy analyses. All observed measurements, excluding post-rescue measurements, of change from baseline in HbA1c through Week 96 will be included in the linear mixed effect model as repeated measures. Intercept and slope for time (entered as continuous variable) will be specified as random covariates, which may be simplified as fixed covariates depending on the assessment of the model fit. The PROC MIXED procedure in SAS will be used. The unstructured correlation for repeated HbA1c change from baseline will be specified; if the model fails to converge, an alternative correlation matrix will be specified.

As with HbA1c, repeated measures analyses will also be performed on change from baseline of body weight, systolic blood pressure, diastolic blood pressure, and FPG. A linear effect model will be utilized for each of the change from baseline measures similarly to that being used for HbA1c change from baseline. All analyses will be performed on the full analysis set.

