- [2] The p-value is from a two-sided t-test for the difference in means of change from baseline.
- [3] Based on ANCOVA: Change = trt + baseline HbAlc + site + age category + gender + race.

Source Data: Listing 16.2-7.1

Programming Note: present for Weeks 2, 6, 12, 18, 24, 36, 48, 60, 72, 84, 96, 97 and 1 week follow-up.

Table 14.2-1.3

Analysis of Change from Baseline in HbA1c (%), Excluding Post-Rescue Values (Full Analysis Set - OC)

Week 2

	EGT0001442	Placebo
	(N=xxx)	(N=xxx)
Number of Subjects [1]	xxx	xxx
Baseline		
Mean (SD)	xx.xx (xx.xxx)	xx.xx (xx.xxx)
Median	xx.xx	xx.xx
Min, Max	xx.x, xx.x	xx.x, xx.x
Week 2		
Mean (SD)	xx.xx (xx.xxx)	xx.xx (xx.xxx)
Median	xx.xx	xx.xx
Min, Max	xx.x, xx.x	xx.x, xx.x
Change from Baseline		
Mean (SD)	xx.xx (xx.xxx)	xx.xx (xx.xxx)
Median	xx.xx	xx.xx
Min, Max	xx.x, xx.x	xx.x, xx.x
p-value [2]	0.xxxx	
Model-Adjusted Change from Baseline [3]		
LS Mean (SE)	xx.xx (xx.xxx)	xx.xx (xx.xxx)
95% Confidence Interval	(xx.xx, xx.xx)	(xx.xx, xx.xx)
Difference from Placebo [3]		
Difference of LS Means	xx.xx	
95% Confidence Interval	(xx.xx, xx.xx)	
p-value	0.xxxx	

Note: This analysis uses observed values excluding those obtained after hyperglycemia rescue; no missing data imputation is performed. \* indicates statistical significance at 0.05 level.

- [1] Number of subjects with a value at baseline and at the specified visit.
- [2] The p-value is from a two-sided t-test for the difference in means of change from baseline.
- [3] Based on ANCOVA: Change = trt + baseline HbAlc + site + age category + gender + race.

Source Data: Listing 16.2-7.1

Programming Note: present for Weeks 2, 6, 12, 18, 24, 36, 48, 60, 72, 84, 96, 97 and 1 week follow-up.

Table 14.2-1.4

Repeated Measures Analysis of Change from Baseline in HbAlc (%) at Week 96, Excluding Post-rescue Values (Full Analysis Set - OC)

	EGT0001442 (N=xxx)	Placebo (N=xxx)
Model-Adjusted Change from Baseline at Week 96 [1]		
n (# of Subjects)	xx	xx
k (# of Post-baseline Visits)	xx	xx
LS Mean (SE)	xx.xx (xx.xxx)	xx.xx (xx.xxx)
95% Confidence Interval	(xx.xx, xx.xx)	(xx.xx, xx.xx)
Difference from Placebo [1]		
Difference of LS Means	xx.xx	
95% Confidence Interval	(xx.xx, xx.xx)	
p-value	0.xxxx	

Note: This analysis uses all observed values excluding those obtained after hyperglycemia rescue; no missing data imputation is performed. \* indicates statistical significance at 0.05 level.

Source Data: Listing 16.2-7.1

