 $\ensuremath{\texttt{[1]}}$  Based on repeated measure model including treatment and visit as factors.

Protocol: THR-1442-C-418 Page x of y

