#### Table 14.2-2.4

Repeated Measures Analysis of Change from Baseline in Fasting Plasma Glucose (mmol/L) at Week 96, Excluding Post-rescue Values

(Full Analysis Set - OC)

Programming Note: See Table 14.2-1.4 for layout. Use footnotes below.

Note: This analysis uses all observed values excluding those obtained after hyperglycemia rescue; no missing data imputation is performed. \* indicates statistical significance at 0.05 level.

[1] Based on repeated measure model including treatment and visit as factors.

Source Data: Listing 16.2-7.2

Protocol: THR-1442-C-418 Page x of y

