#### Table 14.2-3.3

Analysis of Change from Baseline in Weight (kg), Excluding Post-rescue Values (Full Analysis Set- OC)

Programming Note: See Table 14.2-1.3 for layout. Use footnotes below.

Note: This analysis uses observed values excluding those obtained after hyperglycemia rescue; no missing data imputation is performed. \* indicates statistical significance at 0.05 level.

- [1] Number of subjects with a value at baseline and at the specified visit.
- [2] The p-value is from a two-sided t-test for the difference in means of change from baseline.
- [3] Based on ANCOVA: Change = trt + baseline weight + baseline HbA1c category + site + age category + gender + race.

Source Data: Listing 16.2-7.3

Programming Note: present for Weeks 12, 24, 48, 72, 96, 97 and 1 week follow-up.

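### Five repeated-measures shells are titled as Week 96 results, but the model they state gives one pooled treatment difference for all visits; SAP 7.3.1 describes a different model, and LOCF runs past the Week 24 limit in SAP 5.3.1

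*SAP*

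**What the plan says.** **Repeated-measures shells (SAP Appendix 1).** Tables 14.2-1.4 (HbA1c), 2.4 (FPG), 3.4 (weight), 4.4 (systolic) and 5.4 (diastolic) all have Week 96 in the title. Their common layout prints LS means by arm at Week 96, then a difference from placebo with confidence interval and p-value. The model footnote is the same in all five: "Based on repeated measure model including treatment and visit as factors".

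**SAP 7.3.1.** The text describes something else: "Intercept and slope for time (entered as continuous variable) will be specified as random covariates". Both terms can be reduced to fixed ones if the fit suggests it. The section adds: "The unstructured correlation for repeated HbA1c change from baseline will be specified", with another matrix if the model fails to converge. It names neither a visit factor nor a treatment-by-time term.

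**Expected course of the effect.** SAP 5.3.1: "It is expected that 24 weeks of treatment is required to obtain the full treatment effect". It adds that shorter treatment may show only part of the effect.

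**Purpose.** Protocol 9.5.2 gives the HbA1c mixed model the job of assessing an overall treatment effect and then tests each time point separately. The hypothesis is an effect seen at Week 24 and kept up to Week 96.

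**LOCF.** SAP 5.3.1 says that in general LOCF serves endpoints at or before Week 24 and that no analysis imputes beyond it, and refers to Section 7 for detail. Sections 7.2.1 to 7.2.5, 7.3.2 and 7.3.3 ask for LOCF at all visits. The LOCF shells 14.2-1.2, 1.6, 2.2, 2.6, 3.2, 3.6, 4.2, 4.6, 5.2, 5.6, 6.1 and 6.4 run to Week 97 and the one-week follow-up.

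**The concern.** With treatment and visit as the only fixed factors, the model assumes that the arms differ by the same amount at every visit. Software will print that difference under a Week 96 heading, but it draws on every visit from the first one on. It equals the Week 96 effect only if the effect is constant from the first visit (or the errors happen to cancel), and SAP 5.3.1 expects a build-up. A reader who wants to know whether the effect lasted could therefore see a maintained effect understated, or a lost effect shown as present.

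Two programmers could also produce different tables, one from 7.3.1 and one from the footnote. On LOCF, the text does not settle whether the panels after Week 24 should exist. If they do, they show earlier values as late results.

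**Working it through.** **1. Inputs.** From SAP 3.5: difference -0.40 at Week 24, SD 1.0, 150 per arm. These reproduce the plan's own sample size: 2 × (1.960 + 1.282)² × (1.0/0.4)² = 131.3, so 132 per arm by the normal formula and 133 by the t-test, as the SAP states. Nothing below rests on that figure. From the HbA1c shells: 11 post-baseline visits through Week 96 (2, 6, 12, 18, 24, 36, 48, 60, 72, 84, 96), four of them before Week 24.

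Assumed, because the documents give no values: differences of -0.10, -0.20, -0.30, -0.40, -0.40 at Weeks 2 to 24, then a straight line to the stated Week 96 value; SD 1.0 throughout; complete data; correlation exchangeable 0.6, or first-order autoregressive per visit step (AR) 0.8 or 0.9.

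**2. What the additive model estimates.** With complete data and covariance V, the estimated difference is Σ wⱼdⱼ, where dⱼ is the difference at visit j and w = V⁻¹1 / (1′V⁻¹1). The same number applies at every visit. A direct fit to simulated data confirmed it: -0.1953 at all 11 visits, while the arm means moved. This equality needs none of the assumptions above.

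**3. Weights.**
- Exchangeable: 1/11 each.
- AR with correlation ρ: 1/(11 − 9ρ) for the first and last visits, (1 − ρ)/(11 − 9ρ) for the others. For ρ = 0.8 these are 0.263 and 0.053; for ρ = 0.9, 0.345 and 0.034.

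| | Exch. 0.6 | AR 0.8 | AR 0.9 |
|---|---|---|---|
| Weight on the four visits before Week 24 | 0.36 | 0.42 | 0.45 |
| Weight on Week 96 | 0.09 | 0.26 | 0.34 |
| Shown if Week 96 is truly -0.40 | -0.345 | -0.305 | -0.286 |
| Shown if Week 96 is truly 0 | -0.218 | -0.147 | -0.114 |

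Example, exchangeable and maintained: (−0.10 − 0.20 − 0.30 − 8 × 0.40)/11 = −3.8/11 = −0.345. For the fade, Weeks 36 to 96 sum to −1.0, so (−1.4 − 1.0)/11 = −0.218.

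**4. Other assumptions.** A linear rise from 0 to -0.40 by Week 24, with correlations 0.3 to 0.7, gives -0.27 to -0.31 (maintained) and -0.09 to -0.19 (fade to 0). An effect of -0.40 at every visit gives -0.40, with no distortion.

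**5. SAP 7.3.1 as written.** An unstructured 11-visit covariance has 11 × 12/2 = 66 parameters. A random intercept and slope add 3 if correlated, 2 if independent: 69 or 68 where the data identify 66. The model is over-parameterised if all parts are fitted together.

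**6. LOCF count.** Ten of the 12 shells list 8 time points after Week 24 and the two weight shells list 5: 10 × 8 + 2 × 5 = 90 panels.

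**7. Cost of the interaction.** The Week 96 standard error becomes √(2/150) = 0.115. For the additive model it is √[(2/150)/(1′V⁻¹1)]: 1′V⁻¹1 is 11/7 = 1.571 for exchangeable 0.6, giving 0.092, and 3.8/1.8 = 2.111 for AR 0.8, giving 0.079.

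**The case against.** **The footnote may not be the full model.** It lists what the model includes, while the ANCOVA footnotes write out an equation, and 7.3.1 speaks of treatment as an effect over time. A reader might infer that the SAP definitely fits an additive model. The documents do not support that: an unlisted interaction cannot be ruled out. What stands is that none is stated in either place, and a prespecified model should not depend on a guess.

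**Not everything under the title is wrong.** The row that carries the Week 96 label holds the arm means, which do vary by visit. The layout also prints the number of post-baseline visits. Only the difference, its interval and its p-value are affected.

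**Week 96 is already covered.** Table 14.2-1.3 gives by-visit, observed-case contrasts without post-rescue values, and its counterparts do so for the other endpoints. The mixed model is exploratory, with nominal p-values. So a reader should not infer that the trial lacks a valid Week 96 comparison. This objection stands and limits the stakes. In addition, the wording of the durability hypothesis is from the February 2011 protocol, and the SAP shells cite later versions that are not in hand; SAP 2.2 does keep HbA1c change to Week 96 as an objective.

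**LOCF.** A reader might infer that the late LOCF panels plainly breach the SAP. They do not clearly do so: 5.3.1 is worded as a general rule, speaks of carrying values to all remaining visits, and defers to Section 7. The LOCF layouts also print how many values were carried forward. What stands is a contradiction that the text does not resolve.

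**Conclusion.** The point holds as a labelling and specification fault, worth fixing before the Week 96 tables are produced. Fitted as written, the five shells report one pooled difference under a Week 96 title. That follows from the form of the model alone. Its size does not: -0.29 to -0.35 for a maintained -0.40, and -0.11 to -0.22 for a fade to 0, rest on the assumed onset, correlations, SD 1.0 at all visits and complete data.

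The pooled value should not be read as a simple average over visits either. Under two assumed random-intercept-and-slope covariances, the Week 96 weight is negative (-0.04 and -0.07). Those cases have Week 24 SDs of 0.85 and 0.81, not the SAP's 1.0, so they are kept out of the ranges above.

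The mismatch between 7.3.1 and the footnotes, and that between 5.3.1 and Section 7 with its 12 shells, can be read directly from the text. The primary Week 24 test and the sample size are untouched.

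**What to change.** **Model.** In 7.3.1 and the five footnotes, state one model: treatment, categorical visit and treatment-by-visit, with unstructured within-subject covariance, the existing convergence fallback and no added random effects. Report the Week 24 and Week 96 contrasts.

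**Alternative.** If only the Protocol's overall effect is wanted, remove Week 96 from the five titles, call the difference the model-based overall (pooled) treatment effect across visits, and name Table 14.2-1.3 and its counterparts (2.3, 3.3, 4.3, 5.3) as the Week 96 result.

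**LOCF.** Limit LOCF to visits through Week 24 in 7.2.1 to 7.2.5, 7.3.2 and 7.3.3, align 5.3.1 with that, and end all 12 LOCF shells at Week 24. Give per-protocol visits after Week 24 in separately titled observed-case summaries, descriptive and without post-rescue values, as 7.3.3 requires.

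**Weight.** Reconcile the visit schedule before naming a range: SAP 7.2.3 analyses Week 2, but the by-visit weight shells are "present for Weeks 12, 24, 48, 72, 96, 97 and 1 week follow-up".

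**Cost.** Text and shell edits only. The Week 96 HbA1c contrast has a larger standard error, about 0.115 against 0.08 to 0.09 with complete data. It still excludes post-rescue values and relies on data missing at random.

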## Table 14.2-1.5 Summary Statistics for HbA1c (%) (Full Analysis Set - OC)

Screening

	EGT0001442 (N=xxx)	Placebo (N=xxx)
Number of Subjects [1]	xxx	xxx
Screening Mean (SD)	xx.xx (xx.xxx)	xx.xx (xx.xxx)
Median	XX.XX	XX.XX
Min, Max	xx.x, xx.x	xx.x, xx.x

Note: This summary uses all observed values; no missing data imputation is performed. Baseline is defined as the last available assessment on or prior to the first dose of study drug.

[1] For Screening and Week 0 the number of subjects with a value at the specified visit is displayed. For all post-baseline visits, the number of subjects with a value at baseline and at the specified visit is displayed. Source Data: Listing 16.2-7.1

Programming Note: Use page 1 shell for Screening and Week 0, use pages 2 shell for the remaining post-baseline visits (Weeks 2, 6, 12, 18, 24, 36, 48, 60, 72, 84, 96, 97 and 1 week follow-up).

Protocol: THR-1442-C-418 Page x of y

Table 14.2-1.5

Summary Statistics for HbA1c (%)

(Full Analysis Set - OC)

Week 2

	EGT0001442 (N=xxx)	Placebo (N=xxx)
Number of Subjects [1]	xxx	xxx
Baseline		
Mean (SD)	xx.xx (xx.xxx)	xx.xx (xx.xxx)
Median	xx.xx	xx.xx
Min, Max	xx.x, xx.x	xx.x, xx.x
Week 2		
Mean (SD)	xx.xx (xx.xxx)	xx.xx (xx.xxx)
Median	xx.xx	xx.xx
Min, Max	xx.x, xx.x	xx.x, xx.x
Change from Baseline		
Mean (SD)	xx.xx (xx.xxx)	xx.xx (xx.xxx)
Median	xx.xx	xx.xx
Min, Max	XX.X, XX.X	xx.x, xx.x

Note: This summary uses all observed values; no missing data imputation is performed. Baseline is defined as the last available assessment on or prior to the first dose of study drug.

[1] For Screening and Week 0 the number of subjects with a value at the specified visit is displayed. For all post-baseline visits, the number of subjects with a value at baseline and at the specified visit is displayed. Source Data: Listing 16.2-7.1

Programming Note: present for Weeks 2, 6, 12, 18, 24, 36, 48, 60, 72, 84, 96, 97 and 1 week follow-up.

Protocol: THR-1442-C-418 Page x of y

### Table 14.2-1.6 Analysis of Change from Baseline in HbA1c (%) (Per Protocol Analysis Set - LOCF)

Programming Note: See Table 14.2-1.1 for layout. Use footnotes below.

Note: This analysis uses the last observation carried forward (LOCF) method for missing post-baseline values as well as for values obtained after hyperglycemia rescue. \* indicates statistical significance at 0.05 level.

- [1] Number of subjects with a value at baseline and at the specified visit.
- [2] The p-value is from a two-sided t-test for the difference in means of change from baseline.
- [3] Based on ANCOVA: Change = trt + baseline HbAlc + site + age category + gender + race.

Source Data: Listing 16.2-7.1

Programming Note: present for Weeks 2, 6, 12, 18, 24, 36, 48, 60, 72, 84, 96, 97 and 1 week follow-up.

Table 14.2-2.1 Analysis of Change from Baseline in Fasting Plasma Glucose (mmol/L) at Week 24 (Full Analysis Set - LOCF)

Programming Note: See Table 14.2-1.1 for layout. Use footnotes below.

Note: This analysis uses the last observation carried forward (LOCF) method for missing post-baseline values as well as for values obtained after hyperglycemia rescue. \* indicates statistical significance at 0.05 level.

- [1] Number of subjects with a value at baseline and at the specified visit.
- [2] The p-value is from a two-sided t-test for the difference in means of change from baseline.
- [3] Based on ANCOVA: Change = trt + baseline FPG + baseline HbA1c category + site + age category + gender + race.

Source Data: Listing 16.2-7.2

Protocol: THR-1442-C-418 Page x of y

#### Table 14.2-2.2

Analysis of Change from Baseline in Fasting Plasma Glucose (mmol/L) (Full Analysis Set - LOCF)

Programming Note: See Table 14.2-1.2 for layout. Use footnotes below.

Note: This analysis uses the last observation carried forward (LOCF) method for missing post-baseline values as well as for values obtained after hyperglycemia rescue. \* indicates statistical significance at 0.05 level.

- [1] Number of subjects with a value at baseline and at the specified visit.
- [2] The p-value is from a two-sided t-test for the difference in means of change from baseline.
- [3] Based on ANCOVA: Change = trt + baseline FPG + baseline HbA1c category + site + age category + gender + race.

Source Data: Listing 16.2-7.2

Programming Note: present for Weeks 2, 6, 12, 18, 24, 36, 48, 60, 72, 84, 96, 97 and 1 week follow-up.

Protocol: THR-1442-C-418 Page x of y

#### Table 14.2-2.3

Analysis of Change from Baseline in Fasting Plasma Glucose (mmol/L), Excluding Post-rescue Values (Full Analysis Set- OC)

#### Programming Note: See Table 14.2-1.3 for layout. Use footnotes below.

Note: This analysis uses observed values excluding those obtained after hyperglycemia rescue; no missing data imputation is performed. \* indicates statistical significance at 0.05 level.

- [1] Number of subjects with a value at baseline and at the specified visit.
- [2] The p-value is from a two-sided t-test for the difference in means of change from baseline.
- [3] Based on ANCOVA: Change = trt + baseline FPG + baseline HbA1c category + site + age category + gender + race.

Source Data: Listing 16.2-7.2

Programming Note: present for Weeks 2, 6, 12, 18, 24, 36, 48, 60, 72, 84, 96, 97 and 1 week follow-up.

#### Table 14.2-2.4

Repeated Measures Analysis of Change from Baseline in Fasting Plasma Glucose (mmol/L) at Week 96, Excluding Post-rescue Values

(Full Analysis Set - OC)

Programming Note: See Table 14.2-1.4 for layout. Use footnotes below.

Note: This analysis uses all observed values excluding those obtained after hyperglycemia rescue; no missing data imputation is performed. \* indicates statistical significance at 0.05 level.

[1] Based on repeated measure model including treatment and visit as factors.

Source Data: Listing 16.2-7.2

Protocol: THR-1442-C-418 Page x of y

#### Table 14.2-2.5 Summary Statistics for Fasting Plasma Glucose (mmol/L) (Full Analysis Set- OC)

Programming Note: See Table 14.2-1.5 for layout. Use footnotes below.

Note: This summary uses all observed values; no missing data imputation is performed. Baseline is defined as the last available assessment on or prior to the first dose of study drug.

[1] For Screening and Week 0 the number of subjects with a value at the specified visit is displayed. For all post-baseline visits, the number of subjects with a value at baseline and at the specified visit is displayed. Source Data: Listing 16.2-7.2

Programming Note: Use page 1 shell for Screening and Week 0, use pages 2 shell for the remaining post-baseline visits (Weeks 2, 6, 12, 18, 24, 36, 48, 60, 72, 84, 96, 97 and 1 week follow-up).

### Table 14.2-2.6 Analysis of Change from Baseline in Fasting Plasma Glucose (mmol/L) (Per Protocol Analysis Set - LOCF)

Programming Note: See Table 14.2-1.2 for layout. Use footnotes below.

Note: This analysis uses the last observation carried forward (LOCF) method for missing post-baseline values as well as for values obtained after hyperglycemia rescue. \* indicates statistical significance at 0.05 level.

- [1] Number of subjects with a value at baseline and at the specified visit.
- [2] The p-value is from a two-sided t-test for the difference in means of change from baseline.
- [3] Based on ANCOVA: Change = trt + baseline FPG + baseline HbA1c category + site + age category + gender + race. Source Data: Listing 16.2-7.2

Programming Note: present for Weeks 2, 6, 12, 18, 24, 36, 48, 60, 72, 84, 96, 97 and 1 week follow-up.

Protocol: THR-1442-C-418 Page x of y

### Table 14.2-3.1 Analysis of Change from Baseline in Weight (kg) at Week 24 (Full Analysis Set - LOCF)

Programming Note: See Table 14.2-1.1 for layout. Use footnotes below.

Note: This analysis uses the last observation carried forward (LOCF) method for missing post-baseline values as well as for values obtained after hyperglycemia rescue. \* indicates statistical significance at 0.05 level.

- [1] Number of subjects with a value at baseline and at the specified visit.
- [2] The p-value is from a two-sided t-test for the difference in means of change from baseline.
- [3] Based on ANCOVA: Change = trt + baseline weight + baseline HbA1c category + site + age category + gender + race.

Source Data: Listing 16.2-7.3

Table 14.2-3.2

Analysis of Change from Baseline in Weight (kg)

(Full Analysis Set - LOCF)

Programming Note: See Table 14.2-1.2 for layout. Use footnotes below.

Note: This analysis uses the last observation carried forward (LOCF) method for missing post-baseline values as well as for values obtained after hyperglycemia rescue. \* indicates statistical significance at 0.05 level.

- [1] Number of subjects with a value at baseline and at the specified visit.
- [2] The p-value is from a two-sided t-test for the difference in means of change from baseline.
- [3] Based on ANCOVA: Change = trt + baseline weight + baseline HbA1c category + site + age category + gender + race.

Source Data: Listing 16.2-7.3

Programming Note: present for Weeks 12, 24, 48, 72, 96, 97 and 1 week follow-up.

Protocol: THR-1442-C-418 Page x of y

